***Note: Phase I does not require prior CDK 4/6 inhibitor exposure**

***Note: For patients who received prior CDK4/6 inhibition as part of a clinical trial, patients must be unblinded in order to verify that the patient did receive a CDK4/6 inhibitor.**

10. ECOG Performance Status 0 – 1.
11. Radiological evidence of recurrence or progression on or after the last therapy prior to starting study treatment.
12. Patients must have:
 - Measurable disease (based on RECIST 1.1): defined as at least one lesion that can be accurately measured in at least one dimension ≥ 20 mm with conventional imaging techniques or ≥ 10 mm with spiral CT or MRI,
OR
 - Evaluable disease: bone lesions- lytic or mixed (lytic + sclerotic) in the absence of measurable disease
13. Patient has adequate bone marrow and organ function as defined by the following LOCAL laboratory values at screening:

- Absolute neutrophil count $\geq 1.5 \times 10^9/L$.
 - Platelets $\geq 100 \times 10^9/L$.
 - Hemoglobin $\geq 9.0 \text{ g/dL}$.
 - Potassium, total calcium (corrected for serum albumin), magnesium and sodium within normal limits for the institution or corrected to within normal limits with supplements before first dose of study medication.
 - INR ≤ 1.5 or ≤ 2.5 while on anti-coagulant.
 - Estimated glomerular filtration rate (eGFR) $\geq 30 \text{ mL/min/1.73m}^2$ according to the Modification of Diet in Renal Disease (MDRD) formula
 - Serum creatinine $< 1.5 \text{ mg/dL}$ or creatinine clearance $\geq 50 \text{ mL/min}$.
 - Total bilirubin $< \text{ULN}$ except for patients with Gilbert's syndrome who may only be included if the total bilirubin is $\leq 3.0 \times \text{ULN}$ or direct bilirubin $\leq 1.5 \times \text{ULN}$.
 - Alanine aminotransferase (ALT) and aspartate transaminase (AST) $< 2.5 \times \text{ULN}$, except for patients with liver metastasis, who are only included if the AST is $< 5 \times \text{ULN}$.
14. Must be able to swallow ribociclib, everolimus and exemestane capsules/tablets.
15. Patients with metastatic disease are allowed to receive ≤ 28 days of endocrine therapy prior to starting study treatment.

5.3 Exclusion criteria

Patients eligible for this study must not meet any of the following criteria:

1. Patient with visceral crisis or any disease burden that makes the patient ineligible for this study per the investigator's best judgment.
2. Patients who received more than one line of chemotherapy for advanced breast cancer.

****Note: A chemotherapy line in advanced disease is an anticancer regimen(s) that contains at least 1 cytotoxic chemotherapy agent and given for greater 21 days or longer. If a cytotoxic chemotherapy regimen was discontinued for a reason other than disease progression and lasted 21 days or less, then this regimen does not count as a "prior line of chemotherapy"***

3. HER2 overexpression by local laboratory testing (IHC 3+ staining or *in situ* hybridization positive).
4. Patient has received prior treatment with anthracyclines at cumulative doses of 450 mg/m^2 or more for doxorubicin or 900 mg/m^2 or more for epirubicin.
5. Patient with a known hypersensitivity to any of the excipients of ribociclib, mTOR inhibitors, e.g. sirolimus (rapamycin), exemestane.
6. Previous treatment with mTOR inhibitors.
7. Previous treatment with exemestane for metastatic disease (except patients who received ≤ 28 days of exemestane for advanced breast cancer and did not progress).

8. Disease progression on more than one CDK 4/6 inhibitor, or have progressed more than once on the same CDK 4/6 inhibitor.
9. Patient is concurrently using other anti-cancer therapy. All anti-cancer therapy must be discontinued atleast 7 days to study treatment (C1D1). Drugs with overlapping toxicities with either everolimus or ribociclib must also be discontinued at least 7 days prior to C1D1. All AEs related to prior treatment should have resolved to CTCAE version 4.03 Grade ≤ 1 prior to study treatment (including any CDK 4/6 inhibitor).".
10. Patient has not recovered from all toxicities related to prior anticancer therapies to Grade ≤ 1 (based on NCI CTCAE version 4.03). Exception to this criterion: patients with any grade of alopecia and or neuropathy are allowed to enter the study.
11. Patient has had major surgery within 14 days prior to starting study drug or has not recovered from major side effects.
12. Patients with Child Pugh score B or C.
13. Active, bleeding diathesis, or on oral anti-vitamin K medication (except low dose warfarin, Low molecular weight heparin (LMWH) and acetylsalicylic acid or equivalent, as long as the INR is ≤ 2.5 while on anti-coagulant). Fondaparinux is allowed.
14. Radiotherapy <2 weeks prior to starting study treatment. Patients must have recovered from radiotherapy toxicities prior to starting study treatment, and recovered to grade 1 or better from related side effects of such therapy (with the exception of alopecia). Radiotherapy is not allowed at target site following screening.
15. Another malignancy within 3 years prior to starting study treatment, with the exception of adequately treated in-situ carcinoma of the cervix, uteri, basal or squamous cell skin carcinoma.
16. Patients with central nervous system (CNS) involvement unless they are at least 4 weeks from prior therapy completion (including radiation and/or surgery) to starting the study treatment.
17. Patient has impairment of gastrointestinal (GI) function or GI disease that may significantly alter the absorption of the study drugs (e.g., ulcerative diseases, uncontrolled nausea, vomiting, diarrhea, malabsorption syndrome, or small bowel resection).
18. Patient has a known history of HIV infection (testing not mandatory).
19. Patient has any other concurrent severe and/or uncontrolled medical condition that would, in the investigator's judgment, cause unacceptable safety risks, contraindicate patient's participation in the clinical study or compromise compliance with the protocol such as:
 - chronic pancreatitis.
 - active untreated or uncontrolled fungal, bacterial or viral infections, sepsis etc.
 - Uncontrolled diabetes as defined by fasting serum glucose $>1.5 \times$ ULN.
 - Acute and chronic, active infectious disorders including viral and nonmalignant medical illnesses that are uncontrolled or whose control may be jeopardized by the complications of this study therapy.

20. Fasting serum cholesterol >300 mg/dl or 7.75 mmol/L and fasting triglycerides >2.5 × ULN. In case one or both of these thresholds are exceeded, the patient can only be included after initiation of statin therapy and when the above mentioned values have been achieved.
21. Significant symptomatic deterioration of lung function. If clinically indicated, pulmonary function tests including measures of predicted lung volumes, DLco, O₂ saturation at rest on room air should be considered to exclude restrictive pulmonary disease, pneumonitis or pulmonary infiltrates.
22. Active skin, mucosa, ocular or GI disorders of Grade >1.
23. Bilateral diffuse lymphangitic carcinomatosis.
24. Clinically significant, uncontrolled heart disease and/or cardiac repolarization abnormality including any of the following:
 - History of angina pectoris, symptomatic pericarditis, coronary artery bypass graft (CABG) or myocardial infarction within 6 months prior to study entry.
 - Documented cardiomyopathy.
 - Left Ventricular Ejection Fraction (LVEF) <50% as determined by Multiple Gated acquisition (MUGA) scan or echocardiogram (ECHO) detected during screening.
 - History of cardiac failure, significant/symptomatic bradycardia, Long QT syndrome, family history of idiopathic sudden death or congenital long QT syndrome or any of the following:
 - Known risk to prolong the QT interval or induce Torsade's de Pointes.
 - Uncorrected hypomagnesemia or hypokalemia.
 - Systolic Blood Pressure (SBP) >160 mmHg or <90 mmHg.
 - Bradycardia (heart rate <50 at rest), by ECG or pulse.
 - On screening, inability to determine the QTcF interval on the ECG (i.e.: unreadable or not interpretable) or QTcF >450 msec for men and >470 msec for women (using Frederica's correction). All as determined by screening ECG (based on a mean of 3 ECGs).
25. Patient is currently receiving any of the following substances and cannot be discontinued 5 half-lives prior to Cycle 1 Day 1:
 - That have a known risk to prolong the QT interval or induce Torsade's de Pointes.
 - Known strong inducers or inhibitors of CYP3A4/5, including grapefruit, grapefruit hybrids, pummelos, star-fruit, and Seville oranges.
 - Medications that have a narrow therapeutic window and are predominantly metabolized through CYP3A4/5.
26. Not able to understand and to comply with study instructions and requirements.
27. Pregnant or nursing (lactating) women, where pregnancy is defined as the state of a female after conception and until the termination of gestation, confirmed by a positive hCG laboratory test.

28. Sexually active males unless they use a condom during intercourse while taking drug and for 21 days after stopping medication and should not father a child in this period. A condom is required to be used also by vasectomized men in order to prevent delivery of the drug via seminal fluid.

6 Treatment

6.1 Study treatment

For this study, the terms “investigational drug” or “study drug” refer to ribociclib (LEE011). “Investigational treatment”, or “study treatment/group” refers to the triplet combination of ribociclib, everolimus and exemestane. “Study treatment” refers to all drug combinations given during the course of the trial. All dosages prescribed and dispensed to the patient and all dose changes during the study must be recorded on the Dosage Administration Record eCRF.

The investigator or responsible site personnel should instruct the patient to take the study drugs as per protocol (promote compliance). Drug accountability must be performed on a regular basis. Patients will be instructed to return unused study drugs to the site at the end of each cycle. The site personnel will ensure that the appropriate dose of each study drug is administered at each visit and will provide the patient with the correct amount of drugs for subsequent dosing.

In phase I dose escalation (cohort A and B) the subjects will receive everolimus 2.5 mg orally, once daily, and exemestane 25 mg orally, once daily and an increasing/decreasing doses of ribociclib to establish MTD and/or RP2D for Phase II Group 1.

In phase I dose de-escalation (cohort C) the subjects will receive ribociclib 200mg orally, once daily, and exemestane 25 mg orally, once daily and an increasing/decreasing doses of everolimus to establish MTD and/or RP2D for Phase II Group 2.

6.1.1 Dosing regimen

Table 6-1 Dose and treatment schedule for the following combination: ribociclib + everolimus +exemestane (Phase II)

Study treatments	Form and route of administration	Dose	Frequency/regimen
Ribociclib	Capsules/tablets - 50 mg, 200 mg For oral use	RP2D Group 1 or RP2D Group 2	Days 1–28 of each cycle Continuous – no rest days
Everolimus	Tablet - 2.5 mg For oral use	RP2D Group 1 or PR2D Group 2	Days 1–28 of each cycle Continuous – no rest days
Exemestane	Tablet - 25 mg	25 mg	Days 1–28 of each cycle

	For oral use		Continuous – no rest days
Dexamethasone mouthwash (500mL bottle): TID swish and spit (NPO X1 h) for 2 cycles (56 days)			

The study drugs will be administered as a flat-fixed dose, and not by body weight or body surface area. Everolimus and exemestane will be taken orally, once a day every day. Ribociclib will be administered based on RP2D.

6.2 Dose escalation and de-escalation guidelines: Phase I Safety Run-in

The starting doses for the ribociclib + everolimus + exemestane (R-E-E) combination in the dose escalation (cohort A and B) is 250 mg QD for ribociclib, 2.5 mg QD for everolimus, and exemestane at the approved dose of 25 mg QD. The doses of everolimus and exemestane for all patients in this portion will be fixed at 2.5 mg and 25 mg respectively.

The starting doses for the ribociclib + everolimus + exemestane (R-E-E) combination in the dose de-escalation (Cohort C) is 200 mg QD for ribociclib, 5 mg QD for everolimus, and exemestane at the approved dose of 25 mg QD. The doses of ribociclib and exemestane for all patients in this portion will be fixed at 200 mg and 25 mg respectively.

The starting doses of ribociclib and everolimus are based upon a review of the safety, tolerability, and PK observed in the clinical studies outlined in [Section 1.2](#). Because of the potential drug interaction between ribociclib and everolimus that may inhibit the metabolism of everolimus and increase drug exposure by approximately 3-5-fold, the dose of everolimus will be reduced to 2.5mg or 5mg (based on CLEE011X2106 RDE) from the standard dose recommended in the treatment of breast cancer of 10 mg QD ([Section 1.2.2](#)). The starting dose of ribociclib is supported by a recommendation from the CLEE011X2106 study ([Section 1.2.4](#)), CLEE011X2101 study and CLEEX2108 study ([Section 1.2.1.4](#)).

Table 6-2 Dose levels for ribociclib, everolimus and exemestane in Phase I dose escalation (cohort A and B)

Dose Level	Ribociclib	Everolimus	Exemestane
+1 Cohort B	300 mg PO daily	2.5 mg PO daily	25 mg PO daily
1 Cohort A (Start)	250 mg PO daily	2.5 mg PO daily	25 mg PO daily

Table 6-3 Dose levels for ribociclib, everolimus and exemestane in Phase I dose de-escalation (cohort C)

Dose Level	Ribociclib	Everolimus	Exemestane
0 (start)	200 mg PO daily	5 mg PO daily	25 mg PO daily
-1	200 mg PO daily	2.5 mg PO daily	25 mg PO daily

6.2.1 Criteria for dose escalation and determination of MTD(s)/RP2D

6.2.1.1 MTD definition

The MTD is defined as the highest combination drug dosage not causing medically unacceptable DLTs in more than 33% of the treated patients in the first cycle of treatment. AEs and laboratory abnormalities considered to be DLTs are defined in [Table 6-4](#). Only one RP2D will be tested in the Phase II.

In the dose escalation a total of 6 patients will be treated at dose-level 1 (cohort A). Patients must complete a minimum of one cycle of treatment with the minimum safety evaluation and drug exposure or have had a DLT within the first cycle of treatment to be considered evaluable for dose escalation decisions.

- If $\leq 33\%$ of patients experience a DLT in cohort A (dose level 1), the dose will be escalated to the next level cohort B (dose level +1) where 3 patients will be enrolled.
- If $\leq 33\%$ patients experience DLTs in cohort B, an additional 3 patients will be treated at the same dose level.
- If $\leq 33\%$ patients experience a DLT in both cohorts, then the optimal treatment dose based on tolerability and safety profile after two cycles will move into Phase II.
- If $>33\%$ patients experience DLTs in both cohorts, the dose will be de-escalated to the next level down .

Dose escalation and R2PD decisions will be/were made jointly by the independent Data Monitoring Committee, Steering Committee, and Novartis study personnel.

In the dose de-escalation (cohort C), the starting dose of ribociclib and everolimus are based upon a review of the safety, tolerability, and PK observed in the clinical studies outlined in [Section 1.2](#). Because of the potential drug interaction between ribociclib and everolimus that may inhibit the metabolism of everolimus and increase drug exposure by approximately 2-fold, if ribociclib is dosed at 200mg (based on CLEE011X2106) from the standard dose recommended in the treatment of breast cancer of 10 mg QD ([Section 1.2.2](#)). The starting dose of ribociclib is supported by a recommendation from the CLEE011X2106 study ([Section 1.2.4](#))

The MTD is defined as the highest combination drug dosage not causing medically unacceptable DLTs in more than 33% of the treated patients in the first cycle of treatment. AEs and laboratory abnormalities considered to be DLTs are defined in [Table 6-4](#). Only one RP2D will be tested in the Phase II.

Three patients will be treated at dose-level 0 (cohort C). Patients must complete a minimum of one cycle of treatment with the minimum safety evaluation and drug exposure or have had

a DLT within the first cycle of treatment to be considered evaluable for dose escalation decisions.

- If $\leq 33\%$ of patients experience a DLT in cohort C (dose level 0), then an additional 3 patients will be added.
- If $\leq 33\%$ of patients experience a DLT then an expansion phase will be initiated pending approval from DMC.
- If $>33\%$ patients experience a DLT in Dose level 0, the dose will be de-escalated to the next level down (-1). A total of 6 patients with $\leq 33\%$ of patients experience a DLT will be needed in order for dose to be considered for expansion

6.2.2 Definitions of dose limiting toxicities (DLTs)

A dose-limiting toxicity (DLT) is defined as an adverse event or abnormal laboratory value assessed as having a reasonably possible relationship to the study medication(s) and is unrelated to disease, disease progression, inter-current illness, or concomitant medications that occurs within the first 28 days of treatment (cycle 1) with ribociclib + everolimus + exemestane and meets any of the criteria included in [Table 6-4](#). National Cancer Institute Common Terminology Criteria for Adverse events (NCI CTCAE) version 4.03 will be used for all grading.

Whenever a patient experiences toxicity that fulfills the criteria for a DLT, treatment with the study drug combination will be interrupted and the toxicity will be followed up as described in [Section 6.2.3](#). For the purposes of dose escalation and determination of the MTD(s), DLTs that occur during cycle 1 will be necessarily considered, including those in which the event started in Cycle 1 and the confirmation of the DLT occurs in a subsequent cycle. The investigator must notify the Sponsor immediately of any unexpected CTCAE grade ≥ 3 adverse events or laboratory abnormalities. Prior to enrolling patients into a higher dose level, CTCAE grade ≥ 2 adverse events will be reviewed for all patients at the current dose level.

Patients must have completed $\geq 75\%$ of ribociclib + everolimus + exemestane in cycle 1 (≥ 21 days out of 28 days) to be considered for DLT evaluation. Patients not evaluable for DLT could be replaced after discussing with the steering committee.

Appropriate eligibility criteria and specific DLT definitions, as well as specific dose modification and stopping rules are included in this protocol. Recommended guidelines for prophylactic or supportive treatment for expected toxicities, including management of study drug induced adverse events are provided in [Table 6-5](#) and [Table 6-6](#).

For patients who do not tolerate the protocol-specified dosing schedule, dose adjustments are permitted in order to allow the patient to continue the study treatment. These changes must be recorded on the Dosage Administration Record eCRF.

Table 6-4 Criteria for defining Dose Limiting Toxicities

TOXICITY	DLT CRITERIA
	CTCAE grade 3 thrombocytopenia with bleeding

Hematology	Febrile neutropenia (decrease in neutrophils associated with fever $\geq 38.5^{\circ}\text{C}$, ANC $<1.0 \times 10^9/\text{L}$)
	CTCAE grade 4 neutropenia lasting more than 7 consecutive days
	CTCAE grade 4 thrombocytopenia
Gastro-intestinal	CTCAE grade ≥ 3 vomiting ≥ 48 hrs. despite optimal anti-emetic therapy
	CTCAE grade ≥ 3 diarrhea ≥ 48 hrs. despite optimal anti-diarrhea treatment
Hepato-biliary	CTCAE grade ≥ 3 total bilirubin
	CTCAE grade ≥ 2 ALT or AST with total bilirubin $>2.0 \times \text{ULN}$ without evidence of cholestasis***
	OR For subjects with abnormal baseline AST or ALT or total bilirubin value: [AST or ALT >2 x baseline AND $> 3.0 \times \text{ULN}$] OR [AST or ALT $> 8.0 \times \text{ULN}$], whichever is lower, combined with [total bilirubin > 2 x baseline AND $> 2.0 \times \text{ULN}$]
	\geq CTCAE grade 3 ALT for more than 4 consecutive days
Cardiac	Cardiac toxicity \geq CTCAE grade 3
	Clinical signs of cardiac disease, such as unstable angina or myocardial infarction, or Troponin \geq CTCAE grade 3
ECG QT Interval	QTcF interval ≥ 501 ms on at least two separate ECGs
Renal	CTCAE grade ≥ 3 serum creatinine
Stomatitis	CTCAE grade ≥ 4 stomatitis
Hyperglycemia	CTCAE grade ≥ 4 hyperglycemia
Events not	CTCAE grade ≥ 3 , except for the exclusions noted below
Exceptions to DLT criteria	<7 days of CTCAE grade 3 fatigue
	<48 hours of CTCAE grade 3 edema
	Grade 3 laboratory abnormalities that are responsive to oral supplementation or deemed by the investigator to be clinically insignificant
*** "Cholestasis" defined as ALP elevation [$>2.0 \times \text{ULN}$ and R value < 2] in subjects without bone metastasis, or elevation of ALP liver fraction in subjects with bone metastasis)	
Note: (The R value is calculated by dividing the ALT by the ALP, using multiples of the ULN for both values. It denotes whether the relative pattern of ALT and/or ALP elevation is due to cholestatic ($R \leq 2$), hepatocellular ($R \geq 5$), or mixed ($R > 2$ and < 5) liver injury)	
CTCAE version 4.03 will be used for all grading.	
Optimal therapy for vomiting or diarrhea will be based on institutional guidelines, with consideration of the prohibited medications listed in this protocol.	

6.2.3 Follow up for dose limiting toxicities

Patients whose treatment is interrupted or permanently discontinued due to an AE or clinically significant laboratory value must be followed up at least once every 7 days (or more frequently if required by institutional practices, or if clinically indicated) for 30 days, and subsequently

at approximately 30 day intervals, until resolution or stabilization of the event, whichever comes first.

Appropriate clinical experts should be consulted as deemed necessary.

6.2.4 Doses for Phase II

The dose used in Phase II, group 1 recommended by the dose escalation part of this study (Phase I), was determined to be 300mg ribociclib (daily) + 2.5mg everolimus (daily) + 25mg exemestane (daily).

The dose used for phase II, group 2 recommended by the dose escalation part of this study (Phase I), was determined to be 200mg ribociclib (daily) + 5mg everolimus (daily) + 25mg exemestane (daily).

6.2.4.1 Ribociclib, everolimus and exemestane administration

Detailed instructions regarding administration of ribociclib capsules/tablets will be supplied to Investigator sites in a separate document from this protocol.

Complete guidelines for management and administration of exemestane can be found in ([Section 6.4](#)) and the package insert.

Ribociclib, everolimus and exemestane should be taken as follows:

- Patients should be instructed to take the study drug combination of one or more capsules/tablets of ribociclib with one tablet of everolimus and one tablet of exemestane with a large glass of water (~250 mL) daily approximately the same time every day.
- Patients should be instructed to swallow the ribociclib capsules/tablets and everolimus and exemestane tablets whole and not to chew, crush or open them.
- Patients should take all three drugs after eating a light low fat meal
- On days when PK collection/ECG is scheduled at the clinic, patients will take ribociclib, everolimus and exemestane in the clinic under the supervision of the investigator or designee. On all other days patients will take the ribociclib, everolimus and exemestane combination at home.
- If vomiting occurs during the course of treatment, no re-dosing of the patient is allowed before the next scheduled dose. The occurrence and frequency of any vomiting and/or diarrhea (or increase stool frequency) during a treatment cycle must be noted in the adverse events section of the eCRF.
- Any doses that are missed (not taken within 6 hours of the intended time) should be skipped and should not be replaced or made up on a subsequent day.
- Patients must avoid consumption of grapefruit, Seville oranges, grapefruit hybrids, pomelos, star fruit or products containing the juice of each during the entire study and preferably 7 days before the first dose of study medications, due to potential CYP3A4 interaction with the study medications. Orange juice is allowed.

- Herbal or dietary supplements known as strong inhibitors or inducers of CYP3A4/5 or those with a known risk of QT prolongation are not permitted. Multivitamins are permitted. If the potential for interactions are unknown, then the herbal / dietary supplements should be avoided.

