6.4.1.1 Ribociclib (LEE011)

Management of severe or intolerable adverse reactions requires dose reduction, temporary interruption, and/or discontinuation of ribociclib therapy. Each patient is allowed a maximum of two dose reductions for ribociclib. After this, the patient will be discontinued from the study treatment. For each patient, once a dose level reduction for ribociclib has occurred, the dose level may be re-escalated during subsequent treatment cycles once discussed and approved by the sponsor. If a dose reduction is required, ribociclib should be reduced one dose level. Dose levels for ribociclib are provided in [Table 6-5](#).

A dose-dependent DDI was observed between ribociclib and everolimus based on clinical PK analyses in a separate dose escalation trial, where everolimus exposure increased 2- to 4-fold in the presence of ribociclib. If a dose adjustment of both ribociclib and everolimus are required, a dose reduction in ribociclib is considered as a method to reduce exposure to both drugs since everolimus exposure is increased with increased ribociclib doses through a DDI. After permanent discontinuation of either ribociclib, everolimus or exemestane, patients should be discontinued from study treatment. The dose modification guidelines for study treatment are found in [Table 6-5](#) and [Table 6-6](#).

Table 6-5 Phase I dose escalation (cohort A and B) and Phase II group 1: Dose modification guidelines for Ribociclib + everolimus + exemestane

	Ribociclib	Everolimus	Exemestane
	Dose	Dose	Dose
Starting dose	Phase I: refer to cohort A, or B. Phase II cohort 1: 300mg (daily)	2.5 mg daily	25 mg
First dose reduction	Reduced by 50mg	2.5 mg daily	
Second dose reduction	Change current dose to 21days out of 28	2.5 mg daily	

Table 6-6 Phase I dose de-escalation (cohort C) and Phase II cohort 2: Dose modification guidelines for Ribociclib + everolimus + exemestane

	Ribociclib	Everolimus	Exemestane
	Dose	Dose	Dose
Starting dose	200mg daily	If starting at dose level 0: 5mg daily	25 mg

		If starting at dose level -1: 2.5mg daily	
First dose reduction	200mg daily	If starting at dose level 0: 2.5mg daily If starting at dose level -1: 2.5mg every other day	
Second dose reduction	200mg daily	If starting at dose level 0: 2.5mg every other day If starting at dose level -1: discontinue from trial	

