6.6.3 Study drug preparation and dispensation

The investigator or responsible site personnel must instruct the patient or caregiver to take the study drugs as per protocol. Study drug(s) will be dispensed to the patient by authorized site personnel only. All dosages prescribed to the patient and all dose changes during the study must be recorded on the Dosage Administration Record CRF.

Ribociclib will be supplied as capsules or tablets for oral use. The capsules or tablets will be packaged in bottles. Everolimus and exemestane will be supplied as tablets for oral use. Refer to [Table 6-1](#) for ribociclib capsule/tablet and everolimus and exemestane tablet strengths. Ribociclib, everolimus and exemestane will be dosed on a flat scale of mg/day and not adjusted to body weight or body surface area. The dexamethasone mouthwash must be received by designated personnel at the study site, handled and stored safely and properly, and kept in a secured location to which only the investigator and designated site personnel have access. The dexamethasone mouthwash should be stored at 20° to 25°C (68° to 77°F) [see USP Controlled Room Temperature]. Dispense in original, commercial container.

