6.6.4 Study drug packaging and labeling

Ribociclib capsules/tablets are packaged in high density polyethylene (HDPE) bottles with child resistant closures. Everolimus tablets are packaged in blister packs (4 blisters per pack per strength). Exemestane tablets are packaged in high density polyethylene (HDPE) bottles with child resistant closures.

Medication labels will be in the local language and comply with the legal requirements of the United States. They will include storage conditions for the drug but no information about the patient. The medication will be supplied as open label supply to the sites in a way which allows the patient to take medication at home.

Ribociclib capsules/tablets, Everolimus and Exemestane tablets, and dexamethasone mouthwash will be supplied by Novartis.

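### The one-tablet everolimus instruction in protocol 6.2.4.1 and the single 2.5 mg strength in Table 6-1 do not add up to the 5 mg daily dose of Phase II Group 2

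*Protocol*

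**What the plan says.** - **Tablet count.** Protocol 6.2.4.1 instructs patients to take "one or more capsules/tablets of ribociclib with one tablet of everolimus and one tablet of exemestane" once daily. The count is open for ribociclib but fixed at one for everolimus, and the sentence does not distinguish between groups or cohorts.
- **Tablet strength.** The everolimus row of Table 6-1 (6.1.1, headed for Phase II) gives "Tablet - 2.5 mg For oral use". Its dose column reads "RP2D Group 1 or PR2D Group 2", so the one row serves both groups. Section 6.6.3 sends the reader to this table "for ribociclib capsule/tablet and everolimus and exemestane tablet strengths".
- **Assigned dose.** Section 6.2.4 states that the Group 2 dose "was determined to be 200mg ribociclib (daily) + 5mg everolimus (daily) + 25mg exemestane (daily"). Section 6.2 gives the same everolimus dose as the cohort C starting level: the combination "is 200 mg QD for ribociclib, 5 mg QD for everolimus".
- **Reduction level.** For patients who start at 5 mg, Table 6-6 sets the first everolimus reduction as "If starting at dose level 0: 2.5mg daily".
- **Packaging.** Section 6.6.4 says "Everolimus tablets are packaged in blister packs (4 blisters per pack per strength"). It names no second everolimus strength, but it does not exclude one.

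**The concern.** Section 6.2.4.1 is the protocol's instruction on how patients take the drugs, and most doses are taken at home. Read literally with the only strength the protocol lists, it gives Group 2 half of its assigned everolimus.

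The resulting regimen would be ribociclib 200 mg, everolimus 2.5 mg and exemestane 25 mg. That is cohort C dose level -1 in Table 6-3, a different protocol regimen from the one chosen for Group 2. Since the two Phase II groups differ by design in their ribociclib and everolimus doses, an instruction that blurs the everolimus dose affects what Group 2 is meant to test and how its dosing records are read. It does not touch sample size, alpha or power.

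**Working it through.** The check is daily dose = tablets per day × tablet strength, compared with the assigned dose.

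**Inputs**
- Tablets per day: 1 (6.2.4.1).
- Strength: 2.5 mg, the only one listed (Table 6-1).
- Assigned dose: Group 1, 2.5 mg daily; Group 2, 5 mg daily (6.2.4).

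**Group 1, where the text works.** 1 × 2.5 mg = 2.5 mg, equal to the assigned 2.5 mg. The wording also fits cohorts A and B, cohort C level -1, and patients reduced to 2.5 mg daily. The mismatch is therefore specific to the 5 mg dose.

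**Group 2, Table 6-1 taken as complete.**
- As written: 1 × 2.5 mg = 2.5 mg, and 2.5 / 5 = 50% of the assigned dose.
- Tablets needed: 5 / 2.5 = 2 per day.
- Per 28-day cycle: 2 × 28 = 56 needed, against 1 × 28 = 28 as instructed.

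**Group 2, a 5 mg tablet supplied but not listed.** 1 × 5 mg = 5 mg, 100% of the assigned dose. There is no dose error, but Table 6-1 lacks a strength that 6.6.3 says can be found there.

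**Can another passage settle it?**
- The separate administration document mentioned in 6.2.4.1 covers ribociclib. For exemestane the section points to 6.4 and the package insert. It names no such source for everolimus.
- No current passage gives a tablet count for 5 mg or lists a 5 mg tablet.
- The Amendment 1 log records removal of the 1 mg and 5 mg everolimus strengths from Table 6-1. That entry predates cohort C and Group 2 and describes superseded text. It does not show what is supplied now, and this point does not rest on it.

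**Patients concerned.** SAP section 4 reports 46 patients in Group 1 and 33 in Group 2 so far; 46 + 33 = 79, the Phase II count given in Amendment 3. On those figures Group 2 had reached its planned 33, so most first doses were already past. The wording would now matter for Group 2 patients still on full dose, because treatment continues until progression (4.1.2). The documents do not say how many that is. Cohort C level 0 has the same 5 mg dose but is affected less directly, since Table 6-1 is headed for Phase II.

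**The case against.** The strongest reply is that nobody reading the protocol as a whole could mistake the dose. Five milligrams is stated in 4.1, 6.2, 6.2.4 and Tables 6-3 and 6-6, and in SAP section 1.1. The dose column of Table 6-1 itself refers to the recommended Phase II dose. The sentence in 6.2.4.1 is a general how-to-take instruction, while 6.1 makes site staff responsible for the dose given and for the amount sent home. And if a 5 mg tablet is supplied, the instruction is right. All of this stands as a limit on the risk. It does not remove the conflict: either the tablet count or the strength list is wrong for Group 2, and a patient instruction should not depend on staff correcting it.

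Two stronger readings are tempting, and the documents support neither.

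- **That Group 2 was under-dosed.** Nothing shows this. The 50% figure depends on Table 6-1 being complete and on the sentence being followed literally.
- **That one tablet taken at home under a 5 mg record would show only in returned-tablet counts.** The protocol has other safeguards. Patients take everolimus under supervision on PK and ECG clinic days (6.2.4.1, 6.2.4.2, 6.6.6). Everolimus is sampled in all patients on Cycle 1 Day 15, Cycle 2 Days 1 and 15 and Cycle 3 Day 1, with pre-dose samples about 24 hours after the previous dose (7.2.3.1.1, Table 7-6). SAP 3.9 lists and summarises those concentrations. A systematic halving could appear there at group level, although variability would limit detection in a single patient.

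A separate retrospective review of dispensing records would also largely repeat existing requirements. Unused drug is returned each cycle (6.1), compliance is assessed at each visit and the monitor reviews accountability (6.6.6), and the SAP reports dose intensity by component (3.2.1, 3.8.4.5).

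**Conclusion.** The concern holds as a contradiction in the protocol text. Sections 6.2.4.1 and 6.2.4 and Table 6-1 cannot all be correct for Group 2 at full dose. If Table 6-1 is complete, the instruction gives 2.5 mg instead of 5 mg. If an unlisted 5 mg tablet is supplied, the dose is right and the table is incomplete. Which applies depends on the strengths supplied, and the documents do not state that.

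Confidence is high for the text conflict only. The assigned dose is not in doubt, no under-dosing is shown, and the existing controls keep the practical risk small. It is still worth correcting, because it sits in an operative dosing instruction for one of the two Phase II regimens.

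**What to change.** Make one of two changes, according to what is supplied:

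- If only 2.5 mg tablets are supplied, change the everolimus part of the sentence in 6.2.4.1 to *the number of everolimus tablets that delivers the assigned dose (two 2.5 mg tablets for 5 mg)*, and align any patient dosing instructions that repeat it.
- If a 5 mg tablet is supplied, add that strength to the everolimus row of Table 6-1. The revised wording in 6.2.4.1 would still be correct.

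The cost is one phrase or one table entry. No new procedure, data collection or analysis is needed.
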